## **G. Study Procedures**

### **1. Index Visit**

There is no study-determined visit schedule. Patient visits with their PCCs in the randomized clinics will take place without any interference or involvement from the study team. The first visit at which the OUD-CDS algorithms determine that a patient is eligible for the intervention will be denoted as the index visit.

### **2. Treatment/Intervention**

The intervention is the availability of the suicide prevention CDS in approximately half of the parent study's intervention primary care clinics.

### **3. Premature Withdrawal of Participants**

Once randomized, all primary care clinics are anticipated to remain enrolled for the duration of the study. All PCCs in randomized clinics will be followed for the duration of the study unless they die or leave the employment of the clinic. All study-eligible patients with OUD or identified by the algorithms as being at high risk of OUD in randomized clinics will be followed for the duration of the study unless they die or leave the care system. Patients who have opted out of research will be excluded from all analyses.

### **4. Follow-Up**

There is no study-determined visit schedule. Patient visits with their PCCs in the randomized clinics will take place without any interference or involvement from the study team. Primary care visits that take place after the index visit and prior to the end of the observation period will be denoted as post-index visits. The OUD-CDS will flag the occurrence of all index and post-index visits so that EHR data documented from each may be extracted and assembled into an analytic dataset.

## **H. Data Collection and Management**

### **1. Measures of Primary and Secondary Outcomes**

Primary and secondary outcomes will be assessed using the data collected from the EHR via the OUD-CDS and from EHR (Clarity) data pulls.

Primary outcome measures include:

- a) Columbia Suicide Severity Rating Scale (CSSRS): frequency of completion, distribution of CSSRS scores, and Behavioral Health or ED referrals due to CSSRS scores
- b) Frequency and continuity of primary care and mental health visits (post-index visit)
- c) Identification of fatal and non-fatal suicide attempts, using ICD-10 codes
- d) Identification of Opioid overdose, using ICD-10 codes

## **2. Demographics Form**

We will collect age, gender, race/ethnicity, years of practice and medical specialty (primary care vs. internal medicine) for PCC participants. Patient-level data required to assess study objectives will be collected from the EHR by the OUD-CDS and stored in a secure analytic database. Data will be collected from the EHR via the OUD-CDS tool itself, with data stored in a secure server located behind multiple HealthPartners firewalls.

## **3. Contact Information**

We will keep a list of participating primary care clinics, their administrative leaders and their PCCs on a secure server at HealthPartners. This list will include the PCC name, primary care clinic name, phone number of the clinic and provider email address.

## **4. Clinical and Safety Assessments**

This intervention is being delivered by way of CDS prompts to influence provider actions to incorporate evidence-based best practice standards related to both OUD and suicide prevention. Prior to implementation, we will train all intervention PCCs and their rooming staff on the importance of helping us identify any clinician-identified safety events or near-misses that may be related to the EHR or CDS. We will systematically educate them in identification of potential safety events and near-misses and informing us of these events via use of the Feedback Tab in the CDS or email. We will also ask PCCs to notify us of any clinical situations where their clinical judgment differs from the CDS.

Use of the Feedback Tab will automatically generate an email that is sent to study team members, including PIs and programmers. The study team will then discuss this feedback and any necessary actions, and reply to the PCC to answer the question, discuss steps taken to address the issue, or gather additional information if needed to further troubleshoot. PCCs will be asked to submit feedback any time their clinical judgment is inconsistent with the CDS tool. Additionally, the emails of study investigators will be listed on the CDS interface for providers, and PCCs will be encouraged to contact us directly with any questions or concerns if they'd rather not use the Feedback Tab in the OUD-CDS. This feedback will be provided to the DSMB twice per year or at the frequency determined by the DSMB.

### **I. Randomization**

In the parent trial, HealthPartners primary care clinics (n=30) will be randomized to receive or not receive the intervention. In this supplemental study, simple randomization will allocate the intervention clinics (n=15) approximately evenly to receive or not receive access to the MHRN suicide risk models and associated CDS.

Each patient will be considered to belong to the clinic in which his or her first visit that is eligible for the OUD-CDS intervention (i.e., index visit) takes place, and as such will be in the treatment group to which their clinic was randomly assigned. Post-index visits may take place in the same or different clinics or treatment groups relative to the index visit and may or may not be eligible for the OUD-CDS to offer treatment recommendations. In keeping with an intent-to-treat principle, all index and post-index visits and outcome measures for each patient will be attributed to the treatment group assignment of the clinic where the index visit took place.

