**E. Study Design**

**1. Overview of Study Design.** When a patient is at elevated risk of suicide, the PCC will be prompted by Opioid Wizard to complete the CSSRS, easily available to all PCCs in the EHR and saved as discrete data elements. Risk-based (depending on CSSRS score) referral and follow-up recommendations for suicide prevention will be given, with specific care recommendations ranging from care as usual (very low risk) to referral to behavioral health for evaluation and safety planning (moderate to high risk) to immediate evaluation in the emergency department and potential inpatient admission (very high risk), building on workflows developed for use by care managers in our recently completed suicide prevention trial of over 19,000 people at elevated risk of suicide.

The MHRN suicide risk models will be programmed into the EHR, a rigorous process that will take approximately 6 months. This process includes building the model in a testing environment in the EHR, testing the model with fictitious patients in a EHR testing environment and conducting chart audits, revising as needed, testing the model in a different EHR testing environment with real patient data, revising as needed, testing the model by running it silently in the EHR production environment and conducting chart audits, and revising as needed. This is followed by testing in the EHR production environment with 5-15 physicians in 1-2 pilot clinics. Prior to the go-live date for the suicide risk calculator, training on use and interpretation of the suicide risk model and the CSSRS will be provided to all PCCs and their rooming staff in intervention clinics. Training for control clinics will be separate and will provide training on the use of the CSSRS.

**2. Duration of Study and Visit Schedule.** In the parent trial, HealthPartners primary care clinics (n=30) will be randomized to receive or not receive access to the OUD-CDS. In this supplemental study, the clinics receiving access to the OUD-CDS (n=15) will be further randomized (1:1) to receive or not receive access to the MHRN suicide risk models and associated CDS. PCCs in HealthPartners clinics with CDS access will have access to the main OUD-CDS intervention for up to 30 months from date of implementation. PCCs in HealthPartners clinics randomized to the suicide model intervention will have access to the suicide supplement intervention for up to 12 months from date of implementation.

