## F. Study Population

**1. Primary Care Clinics:** For this supplemental study, study clinics will include all 15 HealthPartners primary care clinics randomized to the intervention in the parent study (COMPUTE 2.0); half of these clinics will be randomized to receive access to the suicide risk models and alerts, and half will not. Each primary care clinic has at least 3 eligible PCCs and 50 adult patients who meet inclusion criteria for the parent study (see Section C.6 in the COMPUTE 2.0 Protocol).

**2. Primary Care Clinicians (PCC):** To be eligible for inclusion in the parent study (and therefore also this supplemental study), a PCC must practice at least 0.5 full-time equivalent at a study-eligible primary care clinic and be a family physician, general internist or adult-care non-obstetric nurse practitioner or physician assistant. PCCs are study-eligible regardless of whether they are waivered to prescribe buprenorphine. PCCs in the intervention clinics will be encouraged but not required to use Opioid Wizard with eligible patients; the decision to use or not use the CDS at a given clinical encounter is up the PCC at each clinical encounter.

**Consent:** We will request a waiver of written informed consent from the IRB for PCCs for the intervention, because the CDS is based on current national standards of care and does not make treatment recommendations that are not accepted as community standards of care, and because consenting PCCs would compromise the external validity of the study by introducing selection effects. Our IRB has granted such waivers for similar studies, including the parent study.

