## **3. Statistical Power**

Based on preliminary data, 1619 diagnosed (median=89, range=39-267 per clinic) and 3349 at-risk (median=41, range=19-129) patients were seen in the clinics eligible for the parent study over the course of one year for a total of 4968 (median=130, range=66-387) OUD-CDS-eligible patients. Assuming that 5%, 10% or 20% of approximately 2500 patients are evaluated and considered at high risk for suicide, we estimate that 125 (2500 \* 5%), 250 or 500 patients will be eligible for this study over one year of accrual.

A power analysis estimated the minimum detectable risk ratio for CSSRS and visit rates in intervention relative to control clinics. It relied on data-informed assumptions regarding the number of randomized clinics (n=15) and eligible patients per clinic (pts/clin =8, 16, 33); a range of clinic intraclass correlations consistent with those observed for other process measures at HealthPartners (ICCclin = 0.01, 0.03, 0.05); and outcome likelihood estimates in control clinics (screening=1%, 3%, 5%; visit rate=2, 3, 4/year).

Assuming 3% of control clinic patients are screened for suicide risk, the analysis will be powered (power=0.80,  $\alpha$ 2=0.05) to detect an outcome should at least 14.2% (ICCclin=0.01, 33 pts/clin, risk ratio = 4.72) to 65.0% (ICCclin=0.05, 8 pts/clin, RR=21.66) of intervention clinic patients be screened. The comparable range of detectable differences for outcomes with a 5% screening rate among control clinic patients is 16.8% (RR=3.36) to 54.8% (RR=5.80).

Power for Aim 2 analyses is not as sensitive to sample size assumptions. Under the most generous assumptions (ICCclin= 0.01, 33 pts/clin), small increases in visits rates (2.4 vs. 2.0, RR=1.22; 4.6 vs. 4.0, RR=1.15) will be detectable. Larger but still attainable increases (3.0 vs. 2.0, RR=1.49; 5.3 vs. 4.0, RR=1.33) will be detectable under the most conservative of assumptions (ICCclin=0.05, 8 pts/clin).

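### Simple randomization of 15 clinics does not guarantee the 1:1 or near-even split the plan states; arm sizes should be fixed at 7 and 8

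*Combined protocol and SAP*

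**What the plan says.** Section I (Randomization) names the method and its intended result in one sentence: "simple randomization will allocate the intervention clinics (n=15) approximately evenly to receive or not receive access". Three other places describe the split:

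- Section E.2: "the clinics receiving access to the OUD-CDS (n=15) will be further randomized (1:1) to receive or not receive access".
- Section F.1: "half of these clinics will be randomized to receive access to the suicide risk models and alerts, and half will not".
- Section G.2: the module is available in "approximately half of the parent study's intervention primary care clinics".

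None of them sets the number of clinics per arm, and none mentions blocking, stratification, matching or a balance constraint. Section J.1 handles clinics through a random intercept and names no clinic-level covariate. Section J.3 bases power on 15 clinics with a single patients-per-clinic value in each scenario, and does not state the split between arms.

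**The concern.** Fifteen clinics cannot be halved, and on its own that would be rounding: a reader would take 7 and 8 as meant. The difficulty is the named method. Simple randomization ordinarily means an independent assignment for each clinic, so the arm sizes are themselves random. With hundreds of units that hardly matters; with 15 clusters it does.

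Precision is at stake. A trial of 15 clusters has little to spare, and an uneven split costs power that a different draw would have kept at no expense. Clinic volume is a secondary matter: nothing in the design or model steers how eligible patients divide between the arms.

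**Working it through.** **Inputs.** 15 clinics (sections E.2, I, J.3); power 0.80 and two-sided alpha 0.05; control visit rates of 2 and 4 per year; ICC 0.01 with 33 patients per clinic, or ICC 0.05 with 8 (all J.3).

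**1. The plan's own H2 figures.** J.3 gives detectable visit-rate ratios of 1.22 and 1.15 (ICC 0.01, 33 per clinic) and 1.49 and 1.33 (ICC 0.05, 8 per clinic). I used a Wald test on the log rate ratio with Poisson variance and design effect DE = 1 + (m − 1) × ICC:

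SE² = DE/(k₀ × m × λ) + DE/(k₁ × m × λ × RR), with k₀ control and k₁ intervention clinics.

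For m = 33 and ICC 0.01, DE = 1.32. With k₀ = 7, k₁ = 8, λ = 2, RR = 1.22:

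SE² = 1.32/462 + 1.32/644.16 = 0.00286 + 0.00205 = 0.00491, so SE = 0.0700; ln 1.22 / 0.0700 = 2.84; power = Φ(2.84 − 1.96) = 0.81.

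Solving for 80% power at 7/8 gives ratios of 1.217 and 1.151 (stated 1.22 and 1.15), and 1.474 and 1.324 in the conservative case (stated 1.49 and 1.33). The H2 figures therefore fit a near-even split.

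The H1 range (14.2% to 65.0% against 3%) was not reproduced as a set by any standard two-proportion, log-ratio, log-odds or arcsine formula tried, so nothing below relies on it.

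**2. Splits under independent assignment.** P(split k/(15 − k)) = 2 × C(15, k)/2¹⁵, with 2¹⁵ = 32,768.

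| Split | Calculation | Probability |
|---|---|---|
| 7/8 | 2 × 6,435/32,768 | 39.3% |
| 6/9 | 2 × 5,005/32,768 | 30.5% |
| 6/9 or better | sum of the two | 69.8% |
| 5/10 or worse | 1 − 0.698 | 30.2% |
| 4/11 or worse | 0.302 − 2 × 3,003/32,768 | 11.8% |

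**3. Cost in precision.** With equal variance per clinic, the variance ratio to 7/8 is (1/k + 1/(15 − k))/(1/7 + 1/8), with denominator 0.2679. A design with 80% power at 7/8 has power Φ(2.80/√ratio − 1.96).

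| Split | Variance ratio | SE increase | Power |
|---|---|---|---|
| 6/9 | 0.2778/0.2679 = 1.04 | 1.8% | about 79% |
| 5/10 | 0.3000/0.2679 = 1.12 | 5.8% | about 75% |
| 4/11 | 0.3409/0.2679 = 1.27 | 12.8% | about 70% |

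**4. The same check at the four stated H2 ratios**, using the formula in step 1:

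| Control / intervention clinics | Power |
|---|---|
| 7 / 8 | 0.80 to 0.82 |
| 5 / 10 | 0.74 to 0.76 |
| 10 / 5 | 0.76 to 0.81 |
| 4 / 11 | 0.68 to 0.69 |
| 11 / 4 | 0.71 to 0.77 |

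The loss is larger when the control arm is the small one.

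**5. Volume, illustration only.** J.3 reports "for a total of 4968 (median=130, range=66-387) OUD-CDS-eligible patients", but for the clinics eligible for the parent study. Assume 15 clinics spread over 66 to 387 with median 130. One arm then holds at least two thirds of the patients in about 27% of simple randomizations and about 4% of fixed 7/8 draws; it holds at least 60% in about 52% and 24%. Fixing arm sizes removes most of the extreme imbalance but does not balance volume.

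**The case against.** The strongest reply is that section I can be read as an unstratified draw with arms set at 7 and 8. That reading agrees with all four statements of the split, and on it the arm-size problem disappears. This stands as a possible reading, but the sentence names a method that ordinarily means something else, and no section fixes the arm sizes.

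Even with independent assignment, 6/9 or better occurs 70% of the time and 6/9 costs under 2% in standard error. This also stands: the loss becomes material only from about 5/10, and is smaller when the control arm is the larger one.

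A reader might infer more than the documents support:

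- **That a sixfold range of volume is left uncontrolled in this trial.** The range of 66 to 387 (387/66 = 5.9) covers all OUD-CDS-eligible patients in clinics eligible for the parent study. The spread among these 15 clinics, and among their patients at high suicide risk, is not given.
- **That arm is confounded with clinic type.** Allocation is random and unbiased in expectation, and the random intercept carries between-clinic variation into the standard error. What remains is chance imbalance, and nothing shows that volume predicts CSSRS completion or visit rate.
- **That the draw should also be balanced on baseline CSSRS completion.** At the assumed 1% to 5% in 8 to 33 patients per clinic, the expected count is 0.08 (8 × 0.01) to 1.65 (33 × 0.05) completions per clinic. The constraint would balance mostly noise.

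**Conclusion.** The concern holds in a limited form. The named method does not guarantee the split that the plan states in several places. It would be too strong to say that it fails to deliver the split, since it comes within 6/9 more often than not. Read in its usual sense, it carries a 30% chance of 5/10 or worse (power about 75% instead of 80%) and a 12% chance of 4/11 or worse (about 70% or below).

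The probabilities rest on independent assignment with probability one half per clinic. The power figures rest on equal variance per clinic and equal clinic sizes. That the plan assumed near-even arms is inferred from reproducing its H2 ratios; section J.3 does not say so, and H1 gives no support either way. Any stratification in the parent trial lies outside these documents.

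This does not invalidate the trial. It is an avoidable risk that should be removed, and the method and the stated ratio should agree.

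**What to change.** 1. In section I, replace simple randomization with restricted randomization at fixed arm sizes of 7 and 8: a random draw from the C(15, 7) = 6,435 ways to choose 7 of the 15 clinics, with the arm that receives 8 also chosen at random.
2. In sections E.2 and F.1, change the 1:1 and half-and-half wording to 7/8. The wording in G.2 can stay.
3. Preferably, restrict the draw further to allocations balanced on eligible-patient volume, which the EHR already holds, and include that one variable in the H1 and H2 models in section J.1. The constraint should leave a large share of the 6,435 draws available.

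Steps 1 and 2 need a few lines of code and small wording changes. Step 3 has a small downside: one clinic-level covariate in a model with 15 clusters. For that reason, and given the sparse expected counts, baseline CSSRS completion should not be added as a second balancing variable.

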### **J. Analysis**

#### **1. Study Hypotheses**

**H1:** Opioid Wizard-eligible patients (patients with OUD or at elevated risk of OUD/overdose) with elevated suicide risk in intervention clinics will have higher rates of completed CSSRS assessments than similar patients in control clinics.

**H2:** Opioid Wizard-eligible patients with elevated suicide risk in intervention clinics will have higher rates of engagement in their outpatient mental health care than similar patients in control clinics.

The hypotheses for this supplemental study predict that the Opioid Wizard + Suicide Risk Prediction intervention will increase (a) the likelihood that Opioid Wizard-eligible patients with elevated suicide risk are assessed at the index visit for immediate suicide risk using the CSSRS (H1); and (b) the rate of post-index primary care visits with a mental health diagnosis or with a behavioral health clinician (H2). These hypotheses will be tested using generalized linear mixed models so that each outcome may be estimated among intervention relative to control clinics while accounting for patient outcomes clustered within randomized clinics via a random clinic intercept. Both outcomes will likely be normalized with a Poisson-Normal link function, although the distribution of visits may warrant using a Negative Binomial-Normal link.

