The US Preventative Services Task Force found insufficient evidence to support universal screening for suicide risk, but this is not to discourage screening at-risk populations, such as people with or at high risk for OUD or opioid overdose. A recent commentary in the New England Journal of Medicine states that improved screening for suicide risk along with rapid access to treatment is critical to prevent opioid-related suicide deaths in patients with OUD. Ultimately, people with OUD should be targeted for prevention of both suicide and opioid overdose, recognizing that mental health conditions in this population will further increase risk. To that end, this ancillary study, which will help primary care clinicians (PCCs) both identify people at risk for OUD/opioid overdose and a subset at increased risk of suicide, is particularly timely and important. In addition to guiding PCCs through structured assessment of suicide risk and providing decision support for recognition and treatment of depression, our study's potential to improve access to medications for OUD is also thought to reduce rates of intentional (and unintentional) overdose.

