In both intervention and control clinics, suicide risk scores will be calculated for all Opioid Wizard-eligible patients (at high risk of OUD/overdose or diagnosed with OUD) and archive relevant EHR data to inform analyses. In intervention clinics, Opioid Wizard will alert PCCs to Opioid Wizard-eligible patients who are at increased risk of suicide and coach them through use of the Columbia Suicide Severity Risk Scale (CSSRS), a structured tool in the EHR that will help PCCs assess immediate suicide risk. Based on the resulting CSSRS score, Opioid Wizard will provide EHR links for risk-based referrals and follow-up recommendations, including care as usual, routine or

emergent referral to behavioral health, or transportation to the emergency department for further assessment.

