**Aim 2. Examine the impact of Opioid Wizard + Suicide Risk Prediction on patient engagement in mental health care.**

**H2:** Opioid Wizard-eligible patients with elevated suicide risk in intervention clinics will have higher rates of engagement in their outpatient mental health care than similar patients in control clinics.

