## **4. Exploratory Analyses**

In exploratory analyses, we will also examine (a) intervention effects on outcomes such as depression screening via the Patient Health Questionnaire (PHQ9), suicide attempt, opioid overdose, emergency department visits and hospitalizations, and continuity of care; and (b) treatment effect heterogeneity among patients with OUD who are vs. are not prescribed

OUD medications, and patients with vs. without diagnosed comorbid mental health conditions. Results of this work will provide a workable prototype for timely provision of critically important suicide prevention for patients at risk for or diagnosed with OUD or opioid overdose.

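### H2's pooled visit rate cannot distinguish added mental health care from more diagnosis coding of primary care visits that would have happened anyway

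*Combined protocol and SAP*

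**What the plan says.** Section D (Aim 2) hypothesises that eligible patients in intervention clinics "will have higher rates of engagement in their outpatient mental health care than similar patients in control clinics". Section J.1 repeats this and then defines the tested quantity as "the rate of post-index primary care visits with a mental health diagnosis or with a behavioral health clinician". It is a single rate, analysed with a generalized linear mixed model with a random clinic intercept.

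On what differs by arm, Section D states: "In intervention clinics, Opioid Wizard will alert PCCs to Opioid Wizard-eligible patients who are at increased risk of suicide", followed by coaching through the CSSRS and links for referral. Table 1 in Section F.3 shows no such alerts in control clinics. Section E.1 gives CSSRS training to both arms.

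Section H.1 takes outcomes from EHR data and describes no adjudication. Item (b) of its outcome list names the frequency and continuity of primary care and mental health visits after the index visit, without requiring a diagnosis. Section J.3 plans Aim 2 on control rates of 2, 3 or 4 visits a year and does not divide these between the two visit types.

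**The concern.** The two components of the H2 count are measured differently. A visit with a behavioral health clinician counts because of whom the patient saw. A primary care visit counts because of what the primary care clinician (PCC) recorded.

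The randomised intervention acts on that same clinician. A PCC who has been told that a patient is at elevated suicide risk, and has worked through the CSSRS, may be readier to record a mental health diagnosis. Once recorded, the diagnosis can carry into later visits made for other reasons. Control PCCs get no alert.

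If recording shifts in this way, the pooled rate rises in the intervention arm although patients make no additional visits. The trial could then report improved engagement on the strength of a documentation change.

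**Working it through.** **1. Reproduce the plan's detectable ratios.** Inputs from Section J.3: 15 clinics; 8 to 33 patients per clinic (m); ICC 0.01 to 0.05; power 0.80; alpha 0.05, taken as two-sided (stated for Aim 1, assumed for Aim 2). Also assumed: 7 control and 8 intervention clinics, and one person-year per patient.

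Formula for the log rate ratio, with control rate r0, n0 = 7m, n1 = 8m and DE = 1 + (m − 1) × ICC:

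log(RR) = (1.960 + 0.842) × √[DE × (1/(r0·n0) + 1/(r0·RR·n1))]

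| Case | r0 | Stated RR | Computed RR |
|---|---|---|---|
| Generous (ICC 0.01, m = 33) | 2.0 | 1.22 | 1.217 |
| Generous | 4.0 | 1.15 | 1.151 |
| Conservative (ICC 0.05, m = 8) | 2.0 | 1.49 | 1.474 |
| Conservative | 4.0 | 1.33 | 1.324 |

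The stated 1.49 lies between the normal result and the result with a t distribution on 13 df (1.518). The plan's Aim 2 figures are sound.

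**2. Detectable ratio at the middle planning rate, 3.0 a year.**
- Generous: DE = 1.32, n0 = 231, n1 = 264. 2.802 × √[1.32 × (1/693 + 1/(3 × 1.175 × 264))] = 0.161, so RR = 1.175.
- Conservative: DE = 1.35, n0 = 56, n1 = 64. 2.802 × √[1.35 × (1/168 + 1/(3 × 1.379 × 64))] = 0.321, so RR = 1.379.

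With 8 control and 7 intervention clinics, these become 1.174 and 1.374.

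**3. Ratio produced by coding alone.** Let s be the share of control outcome visits that are diagnosis-coded primary care visits. Let q0 and q1 be the coded shares of all primary care visits in control and intervention. Hold all primary care visits and all behavioral health visits equal between arms. Then

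RR = 1 + s × (q1/q0 − 1), so q1 = q0 × [1 + (RR − 1)/s].

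The documents give neither s nor q0, so both are assumed. Coded share q1 needed to reach the detectable ratio at 3.0 a year:

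| s | q0 = 50%, generous | q0 = 50%, conservative | q0 = 80%, generous |
|---|---|---|---|
| 1.0 | 59% | 69% | 94% |
| 0.75 | 62% | 75% | 99% |
| 0.5 | 68% | 88% | not reachable |

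For s = 1 and q0 = 50%: 0.50 × 1.175 = 58.8% and 0.50 × 1.379 = 69.0%. With q0 = 80%, the conservative case is out of reach even at s = 1 (0.80 × 1.379 = 110%).

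**4. Chance of a significant H2 with no added visit.** This is Φ(log RR/SE − 1.960), where SE is the square-root term in step 1, at the lowest planning rate of 2.0 a year:

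| Coded share | s | RR | Generous | Conservative |
|---|---|---|---|---|
| 50% to 60% | 1.0 | 1.20 | 74% | 24% |
| 50% to 60% | 0.75 | 1.15 | 50% | 16% |
| 50% to 60% | 0.5 | 1.10 | 27% | 10% |
| 80% to 90% | 1.0 | 1.125 | 38% | 12% |
| 80% to 90% | 0.5 | 1.062 | 13% | 6% |

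Steps 1 to 4 credit each patient with a full year. Section F.3 guarantees only three months of follow-up. Shorter follow-up raises the detectable ratio, so larger shifts would be needed and these chances would be lower.

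**The case against.** The strongest reply is that the mechanism is inferred. No section says that the alert prompts a diagnosis. Section C does list "providing decision support for recognition and treatment of depression" among the study's functions, but Section D places depression and anxiety screening support in the parent Opioid Wizard tool. Sections E.2 and F.1 make all 15 clinics parent-intervention clinics, so that support may be present in both arms. Section E.2 also says that the OUD-CDS runs silently in supplement control clinics, which conflicts with this. The depression wording therefore cannot be used to show a between-arm difference. The suicide-risk alert and the CSSRS coaching do differ by arm on any reading.

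Second, a primary care visit with a mental health diagnosis can be genuine outpatient mental health care, and Section D gives primary care an important role in suicide prevention. Counting such visits is defensible. A reader might infer that H2 fails to address Aim 2, or that only behavioral health visits are real engagement. The documents support neither.

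Third, several features limit any bias. The same risk models select patients in both arms, and many may already carry a diagnosis. Coding at the index visit itself is not counted. Under Section I, post-index visits may take place in clinics of the other arm. The behavioral health component dilutes any coding effect.

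Fourth, the plan partly handles the point. Section H.1(b) lists visit frequency without a diagnosis condition, and Section J.4 examines effect heterogeneity by diagnosed mental health comorbidity. Neither is tied to the interpretation of H2.

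These points bear on how large the effect might be. None of them lets the pooled rate tell the two explanations apart.

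**Conclusion.** The point holds as a limit on interpretation. The H2 count includes a component that depends on what PCCs record, the intervention acts on those PCCs in one arm only, and no analysis tied to H2 separates added visits from added coding.

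A reader might go further and conclude that H2 is biased toward the intervention. The documents show that coding could raise the count. They do not show that it will, or by how much. The illustrative thresholds of 59% and 69% assume a base of 3.0 visits a year, a 50% coded share in control, no behavioral health visits in the count and a full year per patient. With half the count made up of behavioral health visits they become 68% and 88%. If coding already starts at 80%, there is little or no room for a shift to reach the detectable ratio. The range runs from a material risk of misreading H2 to a negligible one, and the plan as written would not show which applied.

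**What to change.** Keep the pooled H2 outcome. Prespecify, with estimates and confidence intervals from the same mixed model:

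1. post-index visits with a behavioral health clinician;
2. post-index primary care visits with a mental health diagnosis;
3. all-cause post-index primary care visits.

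Add a sensitivity analysis of (2) restricted to patients with a mental health diagnosis recorded before the index visit. New diagnoses cannot drive that comparison to the same extent, although existing ones may still be coded more often.

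State in advance that a rise in the pooled rate driven by (2) alone, without a rise in (1) or (3), will be reported as possibly reflecting diagnosis recording and not as established added engagement. Do not gate the engagement claim on the direction of (1) alone. With no true effect on (1), chance would satisfy that rule about half the time, and the rule would also refuse the label to real added mental health visits in primary care. Reconcile Section H.1(b) with Section J.1 on what H2 counts.

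The cost is SAP wording and a few more model runs on visit data already listed in Section H.1(b). The downside is precision. By the formula in step 1, at assumed behavioral health rates of 0.5, 1.0 and 1.5 a year, the detectable ratio for (1) would be 1.46, 1.31 and 1.25 in the generous case, and 2.08, 1.71 and 1.56 in the conservative case. The component results should be read as estimates with intervals.
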